2.3 Rationale for dose and regimen selection

EPO treatment is used in MDS patients early after the diagnosis to induce erythroid response and alleviate the symptoms of anemia. At this stage, iron overload is not expected to be high. In addition, the mechanism by which DFX might be efficacious in this setting is related to the depletion of toxic free iron and possibly to the inhibition of NF- κ B in the malignant cells. High doses of DFX are not required to achieve these objectives. Therefore, the dose of DFX DT is established at 10 mg/kg/day and the dose of DFX FCT is established at 7 mg/kg/day.

The current practice for the use of EPO is so variable and differs among countries and even among physicians. Therefore the dose of EPO in this study is chosen based on the guidelines (ASH-ASCO) published by David McCulloch in 2010. According to that, the starting dose in this study is 40,000 units/week. If increase in Hb is < 1 g/dL and total Hb is < 12 g/dL after 4 weeks, the dose should be increased to 60,000 units/week. If increase in Hb is ≥ 1 g/dL and total Hb is < 12 g/dL, patients should continue the current EPO dose. If Hb increase is ≥ 1 g/dL and total Hb is ≥ 12 g/dL, the patients should hold EPO treatment.

Dose change after 12 weeks of study treatment will also be performed according to the EPO guidelines (Appendix 3). If Hb increase is ≥ 1 g/dL and total Hb is < 12 g/dL, patients should continue the current EPO dose. If Hb increase is ≥ 1 g/dL and total Hb is ≥ 12 g/dL, the patients should hold EPO dose (Table 4-1). According to the EPO guidelines, if after 12 weeks of treatment with EPO, Hb increase is < 1 g/dL and total Hb < 12 g/dL, the patient should discontinue EPO as the patient is not responding. In this study, those patients who do not respond to 12-week-EPO treatment will not be discontinued, but they will be switched to the combination for another period of 12 weeks.

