4.1 Description of study design

This is an open-label, phase II, randomized, multi-center, pilot study to assess the efficacy in terms of erythroid improvement of DFX combined with EPO compared to EPO alone in patients with low- and int-1-risk MDS.

Patients will be randomly assigned to DFX plus EPO 40,000 units/week or to EPO 40,000 units/week alone in a 1:1 ratio. The dose of DFX DT will be 10 mg/kg/day and the dose of DFX FCT will be 7 mg/kg/day. At the time when DFX FCT study drug becomes available at a study site, all new patients who are randomized to combination therapy will receive the DFX FCT. Patients who are ongoing and receive DFX DT will continue with the DT. It is not permitted to change formulation during treatment. EPO dose changes after 4 and 12 weeks of study treatment will also be performed in both arms according to the EPO guidelines.

If after 4 weeks, increase in Hb is < 1 g/dL and total Hb is < 12 g/dL, the EPO dose will be increased to 60,000 units/week. If increase in Hb is ≥ 1 g/dL and total Hb is < 12 g/dL, patients will continue the current EPO dose. If Hb increase is ≥ 1 g/dL and total Hb is ≥ 12 g/dL, the patients will hold EPO treatment until end of study (Table 4-1).

If after 12 weeks of treatment with EPO alone, Hb increase is < 1 g/dL and total Hb is < 12 g/dL, the patient will switch to the combination therapy with EPO and DFX. If increase in Hb is ≥ 1 g/dL and total Hb is < 12 g/dL, patients will continue the current EPO dose. If Hb increase is ≥ 1 g/dL and total Hb is ≥ 12 g/dL, the patients will hold EPO treatment until end of study (Table 4-1).

[figure not shown]
If after 12 weeks of treatment with EPO in combination with DFX, Hb increase is < 1 g/dL and total Hb is < 12 g/dL, the patient will be discontinued from the study. If increase in Hb is ≥ 1 g/dL and total Hb is < 12 g/dL, patients will continue the current EPO dose plus DFX. If Hb increase is ≥ 1 g/dL and total Hb is ≥ 12 g/dL, the patients will hold EPO dose and receive treatment with DFX alone.

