Patients will be randomized in a 1:1 ratio at Visit 3 to receive either DFX plus EPO or EPO alone. Study treatment is defined as DFX DT 10 mg/kg/day p.o. or DFX FCT 7 mg/kg/day p.o. plus EPO 40,000 units/week s.c. once weekly or EPO 40,000 units/week once weekly s.c.. The study treatment duration is 24 weeks. After randomization, patient visits will occur weekly during the first month because key safety assessments need to be performed weekly in the first month of treatment and then every 4 weeks thereafter until week 24. In case of a dose increase of EPO to 60,000 units/week after 4 weeks of treatment, an additional visit needs to be performed after 2 weeks of dose increase (Visit 8).

At the time when DFX FCT study drug becomes available at a study site, all new patients who are randomized to combination therapy will receive the DFX FCT. Patients who are ongoing and receive DFX DT will continue with the DT. It is not permitted to change formulation during treatment. Patients will have their first dose of study treatment at Visit 3.

EPO dose adjustments are allowed in both arms according to the EPO guidelines ([Appendix 3](#)). After 4 weeks, if increase in Hb is < 1 g/dL and total Hb is < 12 g/dL, the dose will be increased to 60,000 units/week. If increase in Hb is ≥ 1 g/dL and total Hb is < 12 g/dL, patients will continue the current EPO dose. If Hb increase is ≥ 1 g/dL and total Hb is ≥ 12 g/dL, the patients will hold EPO treatment until end of study ([Table 4-1](#)).

If after 12 weeks of treatment with EPO alone, Hb increase is < 1 g/dL and total Hb is < 12 g/dL, the patient will switch to the combination therapy with EPO and DFX. If increase in Hb is ≥ 1 g/dL and total Hb is < 12 g/dL, patients will continue the current EPO dose; if Hb increase ≥ 1 g/dL and total Hb ≥ 12 g/dL, the patients will hold EPO treatment until end of study ([Table 4-1](#)).

If after 12 weeks of treatment with EPO in combination with DFX, Hb increase is < 1 g/dL and total Hb is < 12 g/dL, the patient will be discontinued from the study. If increase in Hb is ≥ 1 g/dL and total Hb is < 12 g/dL, patients will continue the current EPO dose plus DFX. If Hb increase is ≥ 1 g/dL and total Hb is ≥ 12 g/dL, the patients will hold EPO dose and receive treatment with DFX alone ([Table 4-1](#)).

Table 4-1 EPO Dosing

Initial Treatment	EPO 40,000 units/week	EPO 40,000 units/week + DFX DT 10 mg/kg day or DFX FCT 7 mg/kg day
Week 4	Hemoglobin status	Action

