	Hb increased < 1 g/dL from baseline and Hb < 12 g/dL	Increase EPO to 60,000 units/week *
	Hb increase is ≥ 1 g/dL and Hb < 12 g/dL	Continue EPO 40,000 units/week *
	Hb increase is ≥ 1 g/dL and Hb ≥ 12 g/dL	Hold EPO treatment *
Week 12	Hemoglobin status	Action
	Hb increased < 1 g/dL from baseline and Hb < 12 g/dL	If patient is in the combination arm: Discontinue from the study or If patient is in the EPO monotherapy arm: Switch to the combination EPO + DFX
	Hb increase is ≥ 1 g/dL and Hb < 12 g/dL	Continue current EPO dose *
	Hb increase is ≥ 1 g/dL and Hb ≥ 12 g/dL	Hold EPO treatment *

* Patients in combination arm will continue DFX DT 10 mg/kg/day or DFX FCT 7 mg/kg/day treatment

[figure not shown]
The primary objective (erythroid response according to IWG criteria: Hb increase ≥ 1.5 g/dL) will be assessed at 12 weeks of treatment. At any time, if Hb ≥ 12 g/dL, EPO will be stopped until the end of study.

At 24 weeks, patients initially assigned to the combination therapy who showed Hb increase ≥ 1 g/dL at week 12 will be assessed for full hematological response according IWG criteria (Erythroid response: Hb increase from baseline ≥ 1.5 g/dL; Neutrophil response: increase from baseline of ≥ 100% and > 0.5 x 10⁹/L; Platelet response: increase from baseline of ≥ 30 x 10⁹/L). Patients initially treated with EPO alone and switched to the combination therapy with EPO and DFX after 12 weeks will be assessed for erythroid response according to IWG criteria after 24 weeks.

No RBC transfusions are allowed after randomization, as transfusions would affect the endpoints of the trial. Patients who are RBC transfusion dependent must not be enrolled in the study. RBC transfusion dependence is defined as more than 2 units RBC /4 weeks at any time during the last 12 week period prior to study entry (Gale 2011). Patients must be withdrawn from the study anytime when transfusion as rescue therapy is needed.

Safety assessments are routinely performed including collection of AEs, SAEs, vital signs, physical examination, ECG, hematological and biochemistry assessments.

Patients will continue therapy until disease progression or intolerable toxicity, patient decision or death, after 12 weeks of combination treatment without response or after 24 weeks treatment duration at which point an End of Treatment (EOT) Visit will be performed and the End of Treatment CRF page will be completed.

30 day follow-up

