Patients will commence study treatment with EPO at 40,000 units once weekly. EPO will be provided as available in the respective country. The EPO must be self-administered via the subcutaneous route by the patient or competent personal. The patient will be instructed by the investigator to take the study drug as prescribed. All doses planned and prescribed to the patient and all dose changes including reasons for change during the study must be recorded in the eCRF.

During the regular study visits the investigator or pharmacist will administer to the patient an appropriate number of vials or prefilled syringes, respectively, depending on the local availability. The number of vials or prefilled syringes of each strength dispensed will be recorded in the Study Drug Dosing Log. All EPO medication (used and unused) returned by the patient will be counted and the sum entered in the study drug dosing log by the investigator or pharmacist at the study site.

The initial dose is 40,000 units given subcutaneously once a week. If increase in Hb is < 1 g/dL and total Hb is < 12 g/dL after 4 weeks, the dose will be increased to 60,000 units/week. If increase in Hb is ≥ 1 g/dL and total Hb is < 12 g/dL, patients will continue the current EPO dose. If Hb increase is ≥ 1 g/dL and total Hb is ≥ 12 g/dL, the patients will hold EPO dose (Table 4-1).

If after 12 weeks of treatment with EPO, Hb increase is < 1 g/dL and total Hb < 12 g/dL, the patient will discontinue EPO as the patient is not responding. These patients who do not respond to 12-week-EPO treatment will be switched to the combination for another period of 12 weeks. If Hb increase is ≥ 1 g/dL and total Hb is < 12 g/dL, patients will continue the current EPO dose. If Hb increase is ≥ 1 g/dL and total Hb is ≥ 12 g/dL, the patients will hold EPO dose (Table 4-1).

Instruction how to self-administer subcutaneous injections should be provided by the study personal.

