14.3 Appendix 3: Erythropoietin Treatment and Monitoring Guidelines for MDS patients

Table 14-3 Baseline testing and eligibility criteria for MDS

Required baseline tests	EPO eligibility criteria (CMS)
Hemoglobin	Pretreatment Hb < 10 g/dL
Fe/TIBC (TSAT)	TSAT ≥ 20%
Ferritin	B12 and folate not deficient
B12	Life expectancy > 3 months
Folate	Symptomatic anemia (fatigue, SOB)
	Diagnosis confirmed by cytology or physician
	Marrow blast count is < 5%

Note: Hemoglobin must be done within 1 week prior to EPO treatment

Table 14-4 Initial dosing of EPO for MDS

[figure not shown]
Initial dose
EPO 40,000 units SQ once weekly for 4 weeks
The starting dose in low weight patients with stable anemia - and always in case of reduced renal function - should be lower: 30,000 units weekly
Note: Check blood pressure prior to each dose

Table 14-5 Adjusting EPO dosing for MDS

Week	Hemoglobin status	Action
Week 4	Hb increased < 1 g/dL from baseline and Hb < 12 g/dL	Increase EPO to 60,000 units once weekly for 4 weeks
	Hb increase is ≥ 1 g/dL and Hb < 12 g/dL	Continue current EPO dose
	Hb increase is ≥ 1 g/dL and Hb > 12 g/dL	Hold EPO dose Check CBC weekly until Hb is <12 g/dL. When Hb is <12 g/dL resume EPO at reduced dose (decrease dose 50%). Continue to check CBC weekly.
Week 12	Hb increased < 1 g/dL from baseline and Hb < 12 g/dL Or transfusion requirement has not decreased by 50% resulting in a rate of 2 units per month or less for treatment to continue.	Discontinue EPO, the patient is not responding
	Hb increase is ≥ 1 g/dL and Hb < 12 g/dL	Continue current EPO dose
	Hb increase is ≥ 1 g/dL and Hb > 12 g/dL	Hold EPO dose Check CBC weekly until Hb is < 12 g/dL. When Hb is < 12 g/dL resume EPO at reduced dose (decrease dose 50%). Continue to check CBC weekly.
Maintenance (beyond week 12)	MDS: target Hb level 10–12 g/dL	During maintenance, in case Hb > 12 g/dL, decrease the weekly dose every 8 weeks (recommended schedule: 60-40-30-20-15-10- 5,000 units/week). Median maintenance dose is 30,000 units (range is 5,000–60,000 units/week).

Table 14-6 Recommended monitoring

Test(s)	Frequency	Action
Blood pressure	Before each dose of EPO	hold EPO if BP >160/80
CBC	Every 2 weeks until stable (at therapy initiation and after any dose change of EPO 20% or more) Then monthly	--
FE/TIBC Ferritin	At 1 month (at therapy initiation and after oral iron dose change or after IV ferritin) Then at 3 months Then every 3 months	--

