S21	Epo dose reduced below assigned dose as per protocol for more than 1 week in period week 1-12	Report as PD, include in FAS and Safety Set.
S22	Epo dose reduced below assigned dose as per protocol for more than 1 week in period week 13-24	Report as PD, include in FAS and Safety Set.
S23	Epo dose increased above assigned dose as per protocol for more than 1 week in period week 1-12	Report as PD, include in FAS and Safety Set.
S24	Epo dose increased above assigned dose as per protocol for more than 1 week in period week 13-24	Report as PD, include in FAS and Safety Set
S03	Epo dose maintained at 40.000 units/week and not increased to 60.000 units/week after 4 weeks as per protocol for more than 1 week but Hb increase < 1 g/dL and total Hb < 12 g/dL	Report as PD, include in FAS and Safety Set.
S05	Epo dose increased to 60.000 units/week and not maintained at 40.000 units/week after 4 weeks as per protocol for more than 1 week but Hb increase ≥ 1 g/dL and total Hb < 12 g/dL	Report as PD, include in FAS and Safety Set.
S06	Patient randomized to monotherapy not switched to combination therapy as per protocol or switch delayed for more than 1 week after 12 weeks of treatment but Hb increase < 1 g/dL and total Hb < 12 g/dL	Report as PD, include in FAS and Safety Set.
D12	Patient randomized to combination therapy not discontinued after 12 weeks of treatment as per protocol or discontinuation delayed for more than 1 week but Hb increase < 1 g/dL and total Hb < 12 g/dL	Report as PD, include in FAS and Safety Set.
S10	Patient randomized to combination therapy stopped DFX treatment for more than 1 week in period week 1-12 not as per protocol	Report as PD, include in FAS and Safety Set.
S25	Patient assigned to combination therapy stopped DFX treatment for more than 1 week in period week 13-24 not as per protocol	Reported as PD, include in FAS and Safety Set.
M01	Forbidden concomitant medication as per	Report as PD,

	protocol	include in FAS and Safety Set.
M02	Patient received iron chelation therapy other than the study treatment	Report as PD, include in FAS and Safety Set.
D01	Transfusion during the study but not withdrawn	Report as PD, include in FAS and Safety Set.
D02	Pregnancy during the study, but not withdrawn	Report as PD, include in FAS and Safety Set.
S11	Patient randomized but received wrong study drug	Report as PD, include in FAS and Safety Set.

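### At week 12, Protocol 6.1.1 both stops EPO and switches the patient to a combination that contains EPO, and no section states the EPO dose after the switch

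*Protocol*

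**What the plan says.** The instructions for an EPO-arm patient with a week-12 Hb rise below 1 g/dL and Hb below 12 g/dL are spread over several places.

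- **Protocol 6.1.1, erythropoietin paragraphs:** "the patient will discontinue EPO as the patient is not responding". The next sentence reads "These patients who do not respond to 12-week-EPO treatment will be switched to the combination for another period of 12 weeks". Neither gives an EPO dose.
- **Protocol 4.1 and Table 4-1:** "the patient will switch to the combination therapy with EPO and DFX"; the table's action is "Switch to the combination EPO + DFX". Section 6.1.4 repeats the switch. None of the three gives a dose. Table 4-1 tells patients to stay on their present EPO dose only when Hb has risen by at least 1 g/dL.
- **Protocol 4.1, treatment phase:** "Study treatment is defined as DFX DT 10 mg/kg/day p.o. or DFX FCT 7 mg/kg/day p.o. plus EPO 40,000 units/week s.c. once weekly". The same section raises EPO to 60,000 units/week after week 4 when Hb has risen by less than 1 g/dL and is below 12 g/dL.
- **Protocol Appendix 3 (the EPO guideline), week 12:** "Discontinue EPO, the patient is not responding". Section 2.3 cites this rule and departs from it: "those patients who do not respond to 12-week-EPO treatment will not be discontinued, but they will be switched to the combination".
- **SAP 2.7.2** summarises EPO exposure over 24 weeks for switched patients. In **SAP 4.4**, code S20 makes it a deviation to stop EPO for more than a week in weeks 13-24 without the Hb rise and level that call for a hold. Code S22 is "Epo dose reduced below assigned dose as per protocol for more than 1 week in period week 13-24", and S24 is its counterpart for increases.
- **SAP 2.9.2.2** reports one response proportion for switched patients, with a Clopper-Pearson interval and no split by EPO dose.

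**The concern.** Section 6.1.1 is the dosing section that a site would consult, and it gives two instructions that cannot both be carried out as worded. Stopping EPO follows the guideline table, and Section 4.1 says that EPO changes after weeks 4 and 12 follow the guidelines. Continuing EPO follows every description of the combination. Even a site that settles on continuing finds no dose.

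According to Protocol 2.2, the switch phase exists to show whether adding DFX to EPO works in patients who have not responded to EPO. Protocol 1.1 reports that higher EPO doses improved response in some initial non-responders, so the protocol itself treats EPO dose as relevant to this endpoint. If EPO changes on the day DFX starts, the later Hb course reflects both changes. The deviation codes for weeks 13-24 also need a stated dose to judge against.

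**Working it through.** No figure in the plan bears on this point, so the check compares the texts and then computes the dose change under each reading.

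**1. Stop or continue.** The stop sentence in 6.1.1 agrees with Appendix 3. Against it stand Section 2.3, Sections 4.1 and 6.1.4, Table 4-1, the sentence in 6.1.1 that follows it, SAP 2.7.2 and code S20. A switched patient taken off EPO and not restarted, with Hb still up by less than 1 g/dL and below 12 g/dL, meets S20 after more than one week. Literal compliance with one protocol sentence is thus a reportable deviation under the SAP.

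**2. Dose before the switch.** If the week-4 rule was followed, a patient with a week-4 rise below 1 g/dL and Hb below 12 g/dL is on 60,000 units/week. A switched patient still on 40,000 units/week would, under the same rule, have gained at least 1 g/dL by week 4 and then lost it. Rule-breaking cases also exist: code S03 covers patients wrongly kept at 40,000, and S21 covers reductions in weeks 1-12.

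**3. Dose after the switch.** Change = (dose after - dose before) / dose before; 12-week total = 12 × weekly dose.

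| Reading | From 60,000 units/week | From 40,000 units/week | 12-week total after switch (units) |
|---|---|---|---|
| EPO stopped | -60,000 (-100%) | -40,000 (-100%) | 0 |
| 40,000 from the definition | -20,000 (-20,000/60,000 = -33%) | 0 (0%) | 480,000 |
| Dose carried forward | 0 (0%) | 0 (0%) | 720,000 or 480,000 |

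The third row is not written anywhere for switched patients.

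**4. Deviation codes.** S21 and S23 cover weeks 1-12, where Table 4-1 does set the dose. Only S22 and S24, for weeks 13-24, lack a reference dose for switched patients.

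**5. Size of the group.** Sixty patients randomised 1:1 give about 30 on EPO alone. The documents give no switch rate. Assuming 40-60% switch, the group is 12 to 18 patients (30 × 0.4 to 30 × 0.6). Illustrative 95% Clopper-Pearson intervals are 2.1% to 48.4% for 2 of 12 and 6.4% to 47.6% for 4 of 18. Groups of this size are too small to separate an EPO dose effect afterwards.

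**The case against.** The best reply is that a careful reader can tell what was meant. Section 2.3 says outright that the study departs from the guideline at this step. SAP 2.7.2 and S20 presuppose continued EPO, and the stop sentence can be read as ending EPO monotherapy. The 40,000 units/week in the definition reads most naturally as the starting dose: 6.1.1 calls it the initial dose, Table 4-1 puts it in its starting row, and Table 6-1 lists both 40,000 and 60,000. Read as a standing dose, it would contradict the week-4 increase in both arms. Sections 6.1.3 and 6.3.1 send uncovered dose adjustments to the sponsor for authorisation. The affected result is a descriptive secondary proportion in a pilot, and both changes in the table are decreases, which on the protocol's own account would tend to lower response and not flatter DFX.

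Most of this stands. A reader might infer that sites have three equally supported options, or that every switched patient's result is confounded. The documents support neither: the weight of the text is against stopping, the reset to 40,000 is a weak reading, and a site that carries the dose forward changes nothing.

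The reply does not remove the contradictory sentence from the dosing section, and it does not supply a dose. Inferring that EPO continues says nothing about the level at which it continues.

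**Conclusion.** The point holds as a contradiction in the dosing text and an unstated dose. Protocol 6.1.1 tells sites to stop EPO in patients whom the rest of the plan treats as continuing it, and S22 and S24 cannot be applied to switched patients without a stated dose. The switch-phase response can mix the start of DFX with an EPO change of -33% or -100%, but only in patients whose site changes EPO at that moment. How many that is cannot be known from the documents. The ceiling is the switched group, 12 to 18 patients on the assumed 40-60% switch rate.

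Two stronger conclusions are tempting and do not follow. The primary comparison is not compromised, because it covers the first 12 weeks, before any switch. Nor would a single EPO instruction isolate the effect of DFX: the switch phase has no concurrent control, and Protocol 1.2.2 notes that some responses to EPO appear only with treatment as long as 6 months.

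**What to change.** The sponsor's clinical team should reconcile Protocol 2.3, 4.1 (including Table 4-1 and the study-treatment definition) and 6.1.1 with SAP Table 2-1, so that one EPO instruction, including the dose, applies at the switch. Which instruction is a clinical decision and none is proposed here. Codes S20, S22 and S24 should then refer to it.

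Beside the SAP 2.9.2.2 result, report descriptively how many switched patients had their EPO stopped, lowered, raised or left unchanged at the switch. This also shows patients switched before the clarification. With so few patients it should be read as description and not as a subgroup comparison.

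The cost is a short protocol clarification, revised wording for three deviation codes and a few added rows in one table. No new data are needed: planned and actual EPO doses and reasons for change are already recorded (Protocol 6.1.1 and 10.3, SAP 2.7.2.2). The gain is the removal of one avoidable source of change at the switch.
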